The proposed study will consist of a 5-week double-blind cross-over study trial of tolcapone in 20 people (ages 18-65). The study will be divided into an initial 2 week phase and a second 2 week phase, with one of the 2 week phases consisting of active treatment with tolcapone, and the other 2 week phase consisting of inactive placebo treatment. There will be a one-week wash-out phase between the 2-week treatment phases. Participants will be randomized to receive either tolcapone or placebo during the first 2 week phase on a 1:1 basis. This blinding will be maintained by the IDS pharmacy at the University of Chicago.

Based on a recent single dose tolcapone study for OCD, we should not need longer than two weeks to see an effect (unpublished data). Tolcapone is not an SSRI, so we don't anticipate it taking as long as an SSRI to see an effect. In a study using tolcapone for gambling disorder, effects were shown within the first two weeks of taking the drug (Grant et al., 2013). We do not have enough data to know what the effect size will be. It will likely be underpowered, but 20 active vs. 20 placebo should be sufficient to detect a signal. This will provide data for a future well-powered study.

Subjects:

Inclusion criteria:

- 1) Males and females age 18-65;
- 2) Diagnosis of current OCD based on DSM-5 criteria and confirmed using the clinician-administered Structured Clinical Interview for DSM-5 (SCID);
- 3) Able and willing to provide written consent for participation.

Exclusion criteria:

- 1) Unstable medical illness, including liver disease, as determined by the investigator and liver function test;
- 2) History of seizures;
- 3) Clinically significant suicidality (defined by the Columbia Suicide Severity Rating Scale);
- 4) Baseline score of ≥ 17 on the Hamilton Depression Rating Scale (17-item HDRS);

- 5) Lifetime history of bipolar disorder type I or II, schizophrenia, autism, any psychotic disorder, or any substance use disorder;
- 6) Initiation of psychotherapy or behavior therapy within 3 months prior to study baseline;
- 7) Previous treatment with tolcapone;
- 8) Any history of psychiatric hospitalization in the past year;
- 9) Currently pregnant (confirmed by urine pregnancy test)

Data Handling and Record Keeping

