All subject data will be maintained by the study personnel under the supervision of the principal investigator. All subjects will be seen in the Department of Psychiatry at the University of Chicago Medical Center at [name]. Patient binders will be kept in a locked room only accessible to research staff.

Finance and Insurance

All research will be paid for by the internal departmental funds of the Department of Psychiatry at the University of Chicago. In the event that this research activity results in an injury, treatment will be available, including first aid, emergency treatment and follow-up care as needed. Care for such injuries will be billed in the ordinary manner to the subjects' insurance company. If the subject believes that they have suffered a research related injury, they will be instructed to inform the principal investigator immediately.

Compensation

The study will consist of 4 visits. For participating in the study, participants will receive \$25 per visit to be paid in the form of a check at the completion of the study. Parking vouchers will also be provided for subjects as-needed.

[figure not shown]
Time Line

Recruitment for the proposed study will begin as soon as study drug is available. It is anticipated that all subjects would be entered into the study within approximately 12 months, and that the study would be completed within 15 months of initiation.

Study Design

The study is a 5-week, double-blind, placebo-controlled, pilot study of the safety and efficacy of tolcapone for adults with OCD. All eligible study subjects will go through a 2-week treatment phase during which they will begin tolcapone at 100mg twice a day. Subjects will be

given a matching placebo during the 2-week placebo phase. Subjects will be seen for scheduled study visits every two weeks during the 2-week blinded phases. Subjects will be randomized to either receive either the active or placebo condition during the first 2-week phase, and the remaining condition during the second 2-week phase. Study timeline is outlined below.

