All efficacy and safety assessments will be performed at each visit. Subjects who are not compliant with their use of study medication (i.e. failing to take medication for three or more consecutive days) will be discontinued from the study. Patients who experience a clinically significant adverse event will also be discontinued from the study. Liver diseases will be assessed at the time of subject entry and at the last visit. Subjects will have their blood drawn at baseline and again at the time of study completion to test for liver function.

Due to the pandemic of COVID19, study participants can perform their baseline and follow-up visits online using encrypted Zoom instead of in person visits. All inventories will be assessed. Blood samples, however, will be at the discretion of the study PI. In cases where they are considered medically necessary, the participant can have them drawn locally and submitted to the study team.

Screening Assessments

1. Demographic data and clinical characteristics will be recorded for each subject (baseline visit).
2. Formal screening psychiatric interview for each subject including the Mini International Neuropsychiatric Inventory (24) (baseline visit).
3. Symptom severity at baseline and follow-up visits will be examined using reliable and valid scales:
 - a. *Yale Brown Obsessive Compulsive Scale* (YBOCS) (25) (each visit)
 - b. *Clinical Global Impression severity and improvement scales* (26) (each visit)
 - c. *Sheehan Disability Scale* (27) (baseline and final visit)
 - d. *Hamilton Anxiety Rating Scale* (HAM-A) (28) (each visit)
 - e. *Hamilton Depression Rating Scale* (HAM-D) (29) (each visit)

Yale Brown Obsessive Compulsive Scale (YBOCS) (25). The YBOCS is a reliable and valid 10-item clinician administered scale assessing urge, behavior, and total severity scores.

Clinical Global Impression- Severity and Improvement (CGI) (26). The CGI consists of a reliable and valid 7-item Likert scale used to assess severity and improvement in clinical

symptoms. The CGI severity scale was used at each visit and ranges from 1 = “not ill at all” to 7 = “among the most extremely ill.” The CGI Improvement scale was used at each follow-up visit and ranges from 1 = “very much improved” to 7 = “very much worse.”

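### The COVID-19 provision lets an online participant start tolcapone without the liver function test that exclusion 1 relies on

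*Combined protocol and SAP*

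**What the plan says.** All references are to the combined protocol and SAP.

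- **Subjects, exclusion criterion 1:** "Unstable medical illness, including liver disease, as determined by the investigator and liver function test".
- **Study Design, standard rule:** "Liver diseases will be assessed at the time of subject entry and at the last visit". It continues: "Subjects will have their blood drawn at baseline and again at the time of study completion to test for liver function". Neither sentence carries a condition.
- **Study Design, COVID-19 paragraph:** it says that "study participants can perform their baseline and follow-up visits online using encrypted Zoom instead of in person visits". All rating scales are still to be completed. It then says: "Blood samples, however, will be at the discretion of the study PI". A local draw, sent on to the study team, is available when a sample is judged to be needed on medical grounds.
- **Safety Assessments:** one 8 ml venous sample is taken for liver function at entry, and the procedure is repeated at the final visit.
- **Risks:** tolcapone carries a boxed warning for hepatotoxicity. The protocol judges the risk very low at 200 mg/day for 2 weeks, and participants are also watched for clinical signs of hepatic dysfunction.

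**The concern.** The eligibility criterion has two parts, a judgement and a test. The COVID-19 paragraph makes the test optional for anyone whose baseline visit is online, and it does not say whether exclusion 1 still requires it. Two people applying the protocol in good faith could act differently: one insists on a local draw before dosing, the other enrols on history alone.

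What is at stake is the only laboratory check for existing liver disease before exposure to a drug with a boxed hepatotoxicity warning. The low dose and short course bear on the chance that tolcapone injures a healthy liver. They do not show whether an entrant already has liver disease, which is what exclusion 1 screens for. If the baseline sample is missing, an abnormal result at completion also has no comparator, in a study whose stated goals include safety.

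**Working it through.** The plan states no figure to reproduce. The check sets the relevant texts side by side, followed by simple counting.

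1. **Does the COVID-19 paragraph reach the baseline visit?** Yes. It names baseline and follow-up visits together.

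2. **Which blood samples does the discretion cover?** The readable text describes one kind of blood sample, the 8 ml liver function sample (Safety Assessments). Pregnancy, the other laboratory-type exclusion, is tested on urine (exclusion 9). The discretion therefore applies to the liver function test and to nothing else described.

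3. **Is the baseline sample exempted?** No. The paragraph contrasts the rating scales, which are all to be done, with blood samples, which are discretionary. The local draw depends on a judgement of medical need, and the baseline test is not declared to meet it. No sentence elsewhere restores the requirement for online participants.

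4. **Would a later draw catch an omission?** No. Draws are scheduled only at baseline and completion. A participant who takes placebo first has no scheduled draw between the baseline visit and the tolcapone phase.

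5. **Who is exposed?** Study Design says: "All eligible study subjects will go through a 2-week treatment phase during which they will begin tolcapone at 100mg twice a day". The number 20 comes from the Methodology and Data Analysis sections. In a parallel design with 1:1 allocation about half of any untested entrants would receive the drug; here all of them are due to.

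6. **Counts.**

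| Quantity | Planned | Minimum permitted online |
|---|---|---|
| Liver function tests before first dose | 1 (baseline) | 0 |
| Liver function tests over the whole study | 2 (baseline, completion) | 0 |

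That the baseline test precedes the first dose is inferred from its role in eligibility; the text places it at baseline or entry.

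The number of entrants without a baseline test, *k*, is not given and can lie anywhere from 0 to 20, that is 0/20 = 0% to 20/20 = 100%. Nothing in the documents favours a value within that range.

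7. **Exposure, for proportion.** The dose is 100 mg × 2 = 200 mg/day. The Risks section says hepatotoxicity has been documented with at least 16 weeks of continuous use at 600 mg/day without liver test monitoring. This trial has 200/600 = one third of that dose and 2/16 = at most one eighth of that duration. Lack of monitoring is the third circumstance the protocol cites, and it is the one the COVID-19 paragraph allows to recur.

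**The case against.** The best counter-argument is that the texts can be reconciled. Exclusion 1, the baseline draw and the entry assessment in Safety Assessments were all left unamended, and tolcapone goes only to eligible participants. On that reading exclusion 1 itself makes the baseline test medically necessary, the local-draw route exists to serve it, and the discretion still has content for the completion sample. A paragraph about visit logistics should not be taken to waive half of a named eligibility criterion in silence.

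This reading is possible, and a careful principal investigator may well follow it. But the protocol does not state it. The COVID-19 paragraph is the more specific text, names baseline visits, and sets blood samples apart from what must be done. It supports the waiver reading at least as well, so the conflict is real.

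Two further points stand in part. First, the risk is low on the protocol's own reasoning, which is not disputed here, and other safeguards remain: the investigator's judgement, the watch for clinical signs, and the rule that "Patients who experience a clinically significant adverse event will also be discontinued from the study". None of these is offered as a substitute for the entry test, and the last acts only after exposure. Second, the share of participants affected is unknown, so percentages based on an assumed *k* should carry no weight in judging how serious this is.

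**Conclusion.** The concern holds. As written, the COVID-19 paragraph permits, without directing, the start of tolcapone in an online participant who has not had the liver function test named in exclusion 1. The size is one planned test before the first dose against a permitted minimum of none, in a design where every eligible participant is due to receive the drug. The number affected is unknown, between 0 and 20 of 20, and nothing in the documents shows that anyone was dosed untested.

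The conclusion assumes that the study timeline figure, which is not readable in the available copy, does not contain an overriding rule. The protocol should be changed, because an eligibility safeguard is left open and closing it is cheap. The finding does not contradict the protocol's low estimate of hepatotoxicity risk at this dose and duration.

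**What to change.** Add to the COVID-19 paragraph in Study Design:

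> The PI's discretion does not cover the baseline liver function test. An online participant has it drawn locally, or provides a documented result obtained within [X] days, and the investigator reviews it before randomisation and release of study drug.

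The sponsor sets X. The discretion on visit format and on the completion sample can stay.

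The result window and the review step are more explicit than anything now written for in-person participants. They are included because an online entrant's result comes from outside the clinic and may arrive after the visit. If the sponsor prefers the minimum, a single sentence requiring a liver function result before the first dose, local draw allowed, also closes the gap.

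**Cost.** Two sentences, submitted to the IRB like any amendment. The baseline draw is already planned and the local route already exists. An online participant without a recent result makes one trip to a local laboratory before starting, and a few who cannot do so may be lost to recruitment.

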Sheehan Disability Scale (SDS) (27). The SDS is a three-item, reliable and valid self-report scale that assesses functioning in three areas of life: work, social or leisure activities, and home and family life. Scores on the SDS range from 0 to 30.

Hamilton Anxiety Rating Scale (HAM-A) (28). The HAM-A is a reliable and valid, clinician-administered, 14-item scale that provides an overall measure of global anxiety.

Hamilton Depression Rating Scale (HAM-D) (29). The HAM-D is a valid and reliable, 17-item, clinician-administered rating scale assessing severity of depressive symptoms.

Cognitive Assessments: In addition, subjects will undergo cognitive assessments at baseline. Assessments of cognitive control will be comprised of several valid paradigms (Table 1). These tasks are designed to probe dissociable neural circuitry and cognitive processes likely to be implicated in the pathophysiology of OCD. Task order will be chosen arbitrarily and will be applied consistently across subjects, to minimize possible confounding factors of differences in task order across participants.

Table 1. Neurocognitive Tasks

Task	Target Cognitive Process
MOT	Training Task.
Intra-dimensional/Extra-dimensional Set Shift Task (ID/ED task)	Intra- and extra-dimensional thinking ability. Assesses cognitive flexibility.
Stop-Signal Task of Inhibitory Control	Motor impulsivity and response inhibition.
Tower of London Task	Problem solving and logic task.
Cambridge Gamble Task	Decision making and risk adjustment.

RVP	Visual processing abilities.
SWM	Spatial working memory abilities.

Efficacy Assessments

The primary outcome measure will be the *Yale Brown Obsessive Compulsive Scale (YBOCS)*. The YBOCS is a reliable and valid scale that is frequently used in research to assess symptom severity.

Secondary efficacy measures include

- *The Clinical Global Impression-Improvement and Severity scales (CGI)*
- *Sheehan Disability Scale (SDS)*
- *Hamilton Anxiety Rating Scale (HAM-A)*
- *Hamilton Depression Rating Scale (HAM-D)*.

Safety Assessments

Safety assessments (sitting blood pressure, heart rate, adverse effects, and concomitant medications) will be documented at each visit.

Suicidality will be assessed using the Columbia Suicide Severity Rating Scale. This scale will be performed at every visit. Subjects who endorse suicidal thoughts at any time during the study will be removed from the study and appropriate clinical intervention (e.g. hospitalization) will be arranged.

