Demographic and baseline visit characteristics for tolcapone and placebo groups will be compared using chi-square and analysis of variance to determine if group differences existed at randomization. Given the crossover design, both the placebo and the active tolcapone groups will contain an N of 20. Primary and secondary measures will be examined using repeated-measures ANOVA modeling analyses (PROC MIXED, SAS/STAT Software for Windows, Version8.2, SAS Institute Inc., Cary, NC, USA). The baseline value of the measure being analyzed will be used as a covariate. A time trend (linear) will be included in all models. The difference in the overall level of posttreatment values, the main effect for treatment, will be the test of primary interest. Analyses will be performed on all available data as well as for the completers. All available post-randomization data will be first analyzed and a secondary, supportive analysis of completers will be performed. All comparison tests will be two-tailed and an alpha level of .05 will be used to determine statistical significance given the exploratory nature of the study.

Ethical Considerations

This study will be conducted according to US and international standards of Good Clinical Practice (FDA regulations 21 CFR 312 for IND studies and FDA guidance E6) for all studies. Applicable government regulations and University of Chicago research policies and procedures will also be followed. This protocol and any amendments will be submitted to the

University of Chicago Institutional Review Board (IRB) for formal approval to conduct the study. The decision of the IRB concerning the conduct of the study will be made in writing to the investigator.

REFERENCES

2. Baxter LR Jr, Phelps ME, Mazziotta JC, Guze BH, Schwartz JM, Selin CE. Local cerebral glucose metabolic rates in obsessive-compulsive disorder: a comparison with rates in unipolar depression and in normal controls. *Arch Gen Psychiatry* 1987;44:211-218

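### The Sheehan Disability Scale is scheduled at baseline and final visit only, which conflicts with the each-visit rule and cannot support the crossover analysis set for every secondary measure

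*Combined protocol and SAP*

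**What the plan says.** Four statements in the combined protocol and SAP bear on the Sheehan Disability Scale (SDS).

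- **Screening Assessments, item 3c** gives the schedule as "Sheehan Disability Scale* (27) (baseline and final visit". The YBOCS, CGI, HAM-A and HAM-D in the same list are all marked for each visit.
- **Study Design** states: "All efficacy and safety assessments will be performed at each visit". The same paragraph limits one item: "Liver diseases will be assessed at the time of subject entry and at the last visit".
- **Efficacy Assessments** lists "Sheehan Disability Scale (SDS" among the secondary efficacy measures.
- **Data Analysis** states: "Primary and secondary measures will be examined using repeated-measures ANOVA modeling analyses". It adds that "both the placebo and the active tolcapone groups will contain an N of 20" and that "A time trend (linear) will be included in all models". On analysis sets it says: "All available post-randomization data will be first analyzed and a secondary, supportive analysis of completers will be performed". No sentence exempts the SDS from any of this.

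Methodology gives 20 people allocated 1:1 to the two orders of treatment. Compensation gives four visits. Safety Assessments, writing about the liver blood draw, ties the final visit to study completion.

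**The concern.** A site cannot tell from the text whether to give the SDS at the end of phase 1. That matters because a crossover analysis needs a reading after each condition. If the SDS is read only at the end, the crossover is lost for this measure and it becomes a small parallel-group comparison of phase 2.

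The SDS is the only dedicated functioning scale, and Background and Significance hypothesises better overall functioning. The pilot is also meant to supply data for a later, well-powered study. A phase 2 comparison supplies far less information on functioning, has no SDS for anyone who leaves after phase 1 (if the final visit means study completion), and takes the full effect of any phase 1 carry-over.

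**Working it through.** **1. Observations per condition.** The plan's own figure is 20 per condition. With one reading at the end of each phase, 10 people per sequence × 2 sequences gives 20 tolcapone and 20 placebo values, so the figure is reproduced. Under item 3c only the end of phase 2 is read. That gives 10 tolcapone and 10 placebo values, and 0 of 20 people have both.

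**2. Can the stated model be fitted?** Its fixed terms are intercept, baseline, linear time and treatment.

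- Readings at the end of both phases: the design matrix has rank 4 of 4.
- Final visit only: rank 3 of 4. There is one post-treatment time point, so the time trend cannot be separated from the intercept. Treatment is also completely confounded with sequence.

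**3. Analysis sets.** If the final visit means study completion, a person who leaves after phase 1 has no post-randomisation SDS. The all-available-data analysis then reduces to those who reach the end of phase 2, and the supportive completer analysis adds nothing. If the last visit attended counts, this changes, but the text does not say so for the SDS.

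**4. Precision (illustration).** The documents give no SD, correlation or effect size. Let rb be the baseline-to-final correlation and rp the between-period correlation, each assumed to lie between 0.3 and 0.7. Results are in SD units with two-sided alpha 0.05. The comparator is a standard 2×2 crossover analysis.

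- Final visit only: SE = √(1 − rb²) × √(1/10 + 1/10), 17 df
- Crossover: SE = √[(1 − rp)/2 × (1/10 + 1/10)], 18 df
- Variance ratio = 2(1 − rb²)/(1 − rp)

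| Correlation (rb = rp) | SE, final only | SE, crossover | Variance ratio | 95% CI half-width, final only | 95% CI half-width, crossover | Detectable at 80% power, final only | Detectable at 80% power, crossover |
|---|---|---|---|---|---|---|---|
| 0.3 | 0.427 | 0.265 | 2.6 | 0.90 | 0.56 | 1.27 | 0.78 |
| 0.5 | 0.387 | 0.224 | 3.0 | 0.82 | 0.47 | 1.15 | 0.66 |
| 0.7 | 0.319 | 0.173 | 3.4 | 0.67 | 0.36 | 0.95 | 0.51 |

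If rb and rp vary separately, the ratio runs from 1.5 (rb 0.7, rp 0.3) to 6.1 (rb 0.3, rp 0.7), and the interval is 1.2 to 2.5 times as wide. Simulation with the baseline slope estimated (6,000 trials per setting) gave ratios of 1.56, 3.21 and 6.47 where the formula gives 1.46, 3.00 and 6.07. The formula is therefore slightly favourable to item 3c.

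**5. Early leavers (illustration).** If 4 of 20 left after phase 1, 2 per sequence, the final-visit comparison is 8 versus 8 on 13 df, with half-width 0.77 to 1.03 SD. A crossover on the 16 complete pairs (14 df) has half-width 0.42 to 0.63 SD.

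**6. Carry-over (illustration).** Let the effect be d, with a fraction f of the phase 1 tolcapone effect persisting to the end of phase 2.

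- Final-visit contrast: d − fd = d(1 − f)
- Crossover: the mean of d and d(1 − f) = d(1 − f/2)

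With d = 0.6 SD and f = 0.25 these are 0.45 and 0.525 SD. The shrinkage toward zero is the same for a worsening (−0.45 and −0.525). Only a residual opposite in sign to the effect would enlarge the contrast: f = −0.25 gives 0.75 and 0.675 SD.

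**The case against.** **Item 3c may be deliberate.** It is a specific entry beside four scales marked differently, and a specific schedule normally qualifies a general sentence. The liver assessment in the same paragraph is a similar exception, and the timeline figure is not available. This stands, and it makes the clash with the each-visit sentence the weaker half of the point. It does not help Data Analysis, where the SDS still needs an exemption it does not have.

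**The final visit is not wholly open.** Its use in Safety Assessments points to study completion. That is fair, and it supports the reading used here, under which early leavers have no post-treatment SDS.

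**The crossover comparator is partly inferred.** Data Analysis names no subject, period or sequence term; the within-person comparison is implied by the crossover design and the repeated-measures model. The extremes of 1.5 and 6.1 pair unlike correlations for one scale over five weeks, so 2.6 to 3.4 is the more natural range. With equal loss of people, dropout widens both intervals in about the same proportion. The carry-over example uses assumed values, and the plan does include a one-week wash-out. These points limit the numbers but leave the counts and the rank of the model unchanged.

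**The weight is small.** This is one secondary scale in a pilot that the protocol itself expects to be underpowered. That is correct.

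**Conclusion.** The concern holds. As written, the SDS schedule conflicts with the each-visit rule and, read as an exception, cannot supply the data that Data Analysis requires: 10 and 10 values instead of 20 and 20, no one observed under both conditions, and a time trend that cannot be estimated. These conclusions assume only that the final visit is the end of phase 2 and that the 1:1 allocation yields 10 per sequence.

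A treatment effect can still be estimated from a randomised, baseline-adjusted phase 2 comparison, but it is not the planned analysis. Its cost, under the assumed correlations, is a detectable effect of 0.95 to 1.27 SD instead of 0.51 to 0.78 SD. This should be fixed, with limited weight: the YBOCS and the remaining secondary scales are unaffected.

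**What to change.** Reconcile item 3c, the each-visit sentence and Data Analysis in one of two ways.

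1. **Preferred.** Schedule the SDS at each visit, or at minimum at baseline, end of phase 1 and end of phase 2, and analyse it with the same crossover model as the other scales. This restores the within-person comparison and halves the carry-over bias without removing it. If each visit includes a reading after wash-out, say how the model treats it.
2. **If baseline and final visit is intended.** State in Data Analysis that the SDS is exempt from the N of 20 and the time trend, that it is a baseline-adjusted comparison of the two sequences at the final visit, and whether an early last visit counts as final.

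Option 1 costs a three-item self-report form at one existing visit, or at two under an each-visit schedule, plus a short edit submitted to the IRB as an amendment. The end-of-phase-1 visit is inferred from the four visits and the two-weekly schedule, because the text lists no visit weeks. The documents do not give enrolment status; anyone already finished without that reading would lack it. Option 2 is a text edit only, but leaves the weaker comparison in place.
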